7.6.11 Assessment of the efficacy of blinding

Efficacy of blinding will be assessed two times during the trial duration for research subjects and clinical evaluators: At month 6 and after completion of the trial. These evaluations will be administered in person. Similarly, efficacy of blinding for those investigators/data assessors who perform analysis of neuroimaging and immunological data will be assessed twice: at the beginning of their analysis and at the end. Because some of the data acquired during therapy time-points (especially biological/immunological markers) are likely to be influenced by treatment allocation, investigators performing immunological assays will have no access to clinical/MRI data and vice versa. The only person who will have access to all data simultaneously and who will monitor integrity and technical quality of performed analyses will be the PI. However, the PI will not serve as a clinical evaluator.

7.6.12 Release of allocation code

The allocation code will be provided to the investigators by the NIH pharmacy only after all the required analyses (i.e. all primary and secondary outcome measures) have been collected, research databases have been locked and assessment of blinding has been performed.

8. RISKS/DISCOMFORTS

8.1 Risks associated with Idebenone therapy

There is considerable clinical trial and post-marketing experience indicating that idebenone is well tolerated and has a good safety profile. The most relevant adverse reaction data is provided by a recent placebo-controlled study with 48 Friedreich's Ataxia patients below the age of 18 years. Due to the limited sample, frequencies can not be reliably calculated. The most commonly observed adverse reactions were gastrointestinal disorders. The following reactions were observed in more than one patient: headache, diarrhea, nausea and dyspepsia. The following reactions were not observed in more than one patient at the recommended doses: white blood cell count decrease,

disturbance in attention, angina pectoris, vomiting, reflux oesophagitis, musculoskeletal chest pain, myalgia, chromaturia, upper abdominal pain.

Clinical trials with idebenone have previously been performed in indications other than FRDA, predominantly in older patient populations (mainly in Alzheimer's dementia) not readily comparable with FRDA. Besides some of the reactions listed above, patients in these trials showed the following reactions uncommonly (between 1/1000 and 1/100): sleep disorders, nervousness, dizziness, changes in hepatic laboratory values and influenza-like symptoms. These reactions may be more likely in this elderly study population with CNS impairment and more concomitant medications.

Idebenone has not been administered (to our knowledge) to patients with presumed immune-mediated disorders and therefore the effect of idebenone on dysregulated immune responses in humans is currently unknown and difficult to predict. Because several functions of the immune system are dependent of the formation of ROS, a potent antioxidant may theoretically inhibit these functions. Among these are oxidative burst used by granulocytes and monocytes/macrophages to kill intracellular pathogens and granzyme A-, B- and K-mediated killing utilized by natural killer (NK) cells and some T cells. Granzyme-B mediated killing is only partially dependent on the formation of ROS, as it predominantly relies on activation of caspases. Because some of these immune functions (oxidative burst of monocytes/macrophages, including microglia and granzyme-B-mediated killing by cytotoxic T cells) are thought to contribute to CNS tissue damage in MS, theoretical inhibition of these functions by idebenone may have an overall beneficial effect in PP-MS patients.

Inhibition of oxidative burst utilized by granulocytes and monocytes/macrophages can theoretically lead to increased rates of infections; however, this was not observed in double-blinded placebo controlled randomized trials, including those that targeted elderly and disabled patients (e.g. AD), which are known to be more susceptible to infectious complications. Therefore, idebenone is considered to be a safe and well tolerated agent.

Idebenone at high doses (60-75 mg/kg/day or about 3600-4500 mg/day) may cause orange discoloration of urine in few patients. It is unclear if this will occur at the dose of 2250mg/day. The orange discoloration of urine is completely harmless and urine will be monitored every 6 months by urinalysis in order to ensure that hematuria or hemoglobinuria is not mistaken for the orange discoloration due to idebenone.

8.2 Risks of lymphocytapheresis

Adverse reactions associated with lymphocytapheresis include vasovagal syncope with needle insertion and rare hypotension secondary to volume depletion. Because of the controlled nature of these procedures hypotension is unlikely. Exclusion of patients with a history of cardiovascular disease further reduces the risk of this complication. The blood thinner used to prevent blood clots from apheresis can cause mild muscle cramps. If these side effects occur, we can slow down blood flow or use a different blood thinner. If the symptoms do not go away, the apheresis can be stopped. There may also be bruising at the site of needle insertion. Infection is a potential risk, but is unlikely due to the closed system and the maintenance of sterile technique. The Blood Bank has extensive experience with these procedures and has encountered no serious side effects.

8.3 Risks of MRI

People are at risk for injury from the MRI magnet if they have pacemakers or other implanted electrical devices, brain stimulators, dental implants, aneurysm clips (metal clips on the wall of a large artery), metallic prostheses (including metal pins and rods, heart valves, and cochlear implants), permanent eyeliner or tattoos, implanted delivery pump, or shrapnel fragments. Welders and metal workers are also at risk for injury because of possible small metal fragments in the eye, of which they may be unaware. All subjects will be screened for these conditions prior to the study, and if they have any, they will not receive an MRI scan.

Gadolinium is a contrast agent approved for use with MRI by the FDA. No serious side effects have been associated with its use. The effect of gadolinium on the developing fetus remains partly unknown. Animal studies have shown a delay in development but no developmental abnormalities. Consequently, women of childbearing potential will be entered into this study only if an effective means of birth control is in use. A pregnancy test will be done prior to beginning the study and monthly pregnancy tests will be done before MRIs are performed. The risks of an IV catheter include bleeding, infection, or inflammation of the skin and vein with pain and swelling. Symptoms from the contrast infusion are usually mild and may include coldness in the arm during the injection, a metallic taste, headache, and nausea. In an extremely small number of patients, more severe symptoms have been reported including shortness of breath, wheezing, hives, and lowering of blood pressure. Subjects should not receive gadolinium-based contrast agents if they have previously had an allergic reaction to them. Subjects will be asked about such allergic reactions before a contrast agent is administered. People with kidney disease are at risk for a serious reaction to gadolinium contrast called “nephrogenic systemic fibrosis” which has resulted in a very small number of deaths. If patients are older than 60 or have diabetes, kidney disease or liver disease, bloodwork to assess kidney function will be performed within 4 weeks before any MRI scan with gadolinium contrast. Patients may not receive gadolinium for a research MRI scan if kidney function is not normal. The long term effect of noise exposure from MRI is not known.

8.4 Risks of lumbar puncture

Adverse effects associated with lumbar punctures include brief pain or tingling paresthesias radiating down the lower extremity due to the needle brushing against a nerve. Should this occur, the needle can be repositioned. Mild lower back pain at the site of needle insertion following the procedure can occur; this can be managed with over the counter non-steroidal anti-inflammatory agents if needed. In approximately one third of patients, a post-dural puncture headache may develop and persist for a few days; in one in 50 to 200 lumbar punctures the post-dural puncture headache can last longer than 7 days. Generally this headache is not severe and resolves spontaneously within days - 2 weeks. Should the headache persist or be severe, a blood patch can be performed. An extremely rare complication of lumbar puncture includes temporary double vision related to abducens nerve palsy, and infection. Strict aseptic technique will be followed. Collecting additional 10-15 cc of CSF per procedure represents negligible risk (Evans, Armon et al. 2000). In humans the rate of CSF synthesis is approximately 21.5 cc/hour (Kimelberg 2004), or approximately 500cc/24hours, which represents roughly 4 times the total volume of CSF in an adult patients. Therefore, the volume of 20-30cc of CSF that would be collected for both diagnostic and research purposes will be replenished in its entirety within approximately 1-1.5 hours after collection.

Lumbar puncture may be done in the radiology department under fluoroscopic guidance for patient medical or scheduling needs. The total radiation exposure during the 2 procedures is 0.046 rem, which is well below the guideline of 5 rem per year allowed for research subjects by the NIH Radiation Safety Committee.

8.5 Risk of OCT

There are no known medical risks of optical coherence tomography.

8.6 Risk of electrophysiological studies

8.6.13 Risk of TMS

TMS is a safe procedure that has been used on thousands of people throughout the world, particularly the single-pulse TMS used in this study. Most people do not find the stimulation painful, but sometimes strong contractions of scalp muscles can cause discomfort or headache. Headaches usually go away promptly with nonprescription medication. The noise of the TMS magnet may damage hearing, therefore the subjects will be fitted with earplugs that must be worn during TMS. TMS can interfere with implanted medical devices and will not be done in people who have pacemakers, implanted pumps, or stimulators, such as cochlear implants or in people who have metal objects inside the eye or skull.

8.6.14 Risk of nerve conduction studies

The risks of the electrical stimulation using commercial isolated stimulators are low. Most subjects find electrical nerve shocks to be mildly uncomfortable; it is usually perceived as a brief stinging or tapping sensation. The intensities required for nerve conduction studies are usually well tolerated.

8.7 Risk of skin biopsy

Pain at the biopsy site is usually minimal; bleeding and infection are rare. The biopsy site usually heals with a very small, nearly unnoticeable scar, but may leave a raised scar or visible lump.

8.8 Risk Rehab Evaluation

The risk of physical injury in this series of noninvasive tests is minimal.

9. SUBJECT MONITORING

9.1 Parameters to be monitored

9.1.15 Expected Adverse Events

Animal studies predict a low human toxicity profile for idebenone. This is supported by extensive experience including phase I trials in normal human volunteers and phase II and III trials in patients with Alzheimer's disease, Friedreich's Ataxia, cerebrovascular accident (stroke), multi-infarct dementia, and other neurodegenerative diseases (e.g. Huntington's disease). The most frequently and consistently experienced adverse reactions reported across these trials have been headache, diarrhea, nausea and dyspepsia. Events (reported by $\geq 3\%$ of patients) across double-blinded

placebo controlled randomized trials included abdominal pain (8.9%), diarrhea (6.6%), flu-like syndrome (5.5%), accidental injury (4.6%), depression (4.6%), upper respiratory tract infection (4.5%), headache (3.9%), back pain (3.7%), agitation (3.5%), urinary tract infection (3.2%), and dizziness (3.0%). The events occurred with similar frequency in patients receiving placebo and thus were not felt to be drug related. These events are typically mild to moderate in severity and reversible. A complete list of previous adverse events, which may also be expected in this trial, may be found in the Investigator's Brochure and is summarized in section 7 of that document. In addition, medical events typical for clinical course of PP-MS (i.e. typical neurological signs/symptoms that patient experienced during pre-treatment baseline and their worsening as would be expected from the natural history of PP-MS) can be regarded as expected events in the course of the current trial.

9.1.16 Monitoring of adverse events

The patient will be instructed to contact the investigator immediately should the patient manifest any sign or symptom perceived as serious during the period extending from performance of the first study procedure (e.g. drawing of a blood sample) up to and including 1 month after the last dose (telephone interview at month 25). After this period of time, the patient should report to the investigator only adverse events that are serious and perceived as possibly related to their participation in this study.

Additionally, the patient will be instructed to contact the investigator immediately if he/she believes that he/she has fathered/conceived a child. Testing would be performed to verify that the subject or subject's partner was pregnant. If the pregnancy test were positive, the patient would be instructed to immediately stop taking the study drug and his/her treatment assignment would be revealed to the investigators and the DSMB. The patient or partner would be counseled and followed closely during the pregnancy by the NIH research team and would implement any recommendations made by the DSMB.

Patients will be physically examined by the investigator approximately every 6 months for the study duration. Extensive laboratory monitoring of the following will occur every 6 months for the study duration: CBC with differential, Chemistry panel 20, and urinalysis and pregnancy test (for females with childbearing potential). Additionally, laboratory monitoring (CBC, chemistry panel with liver function tests) will be performed every 3 months after initiation of dosing of idebenone for the first year of treatment and every 6 months thereafter.

All adverse events occurring within 1 month following the last administration of the study medication must be recorded on the Adverse Event Form irrespective of severity and seriousness, and whether or not they are considered related to the study medication. Additionally, all serious adverse events (SAE) brought to the attention of the investigator during the period starting from the day of performance of the first study procedure to the telephone interview on month 25, must be recorded and reported to the FDA in accordance with federal regulations and NIH procedures. Any SAE reported by the patient after month 24, will be subjected to expedited reporting only if judged to be related to the study treatment by the Investigator.

The collection of complete and accurate information is of paramount importance to allow a full evaluation of SAEs. Each SAE will be properly documented and followed up until the event is resolved, subsided, stabilized, disappeared or is otherwise explained or the study patient is lost to

follow-up. Recurrent episodes, complications, or progression of the initial SAE will be reported as follow-up to the original episode, regardless of when the event occurs. Follow-up of reportable SAEs will be submitted to the FDA, IRB and Santhera Pharmaceuticals (Switzerland) Ltd. according to the same timelines mandatory for initial reports. An SAE that is considered completely unrelated to one previously reported, will be reported separately as a new event.

NINDS will provide Santhera Pharmaceuticals (Switzerland) Ltd. with copies of all Serious Adverse Drug Reaction reports concurrently with their submission to the FDA, including copies of any warning letters or other information affecting the safety and/or well-being of human subjects in research conducted under this CTA.

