9.2.20 Assessment of causality

Every effort should be made by the investigator to explain each adverse event and assess its causal relationship, if any, to the study medication. The degree of certainty with which an adverse event can be attributed to the study medication (or alternative causes, e.g. natural history of the underlying diseases, concomitant therapy, etc.) will be determined by how well the event can be understood in terms of one or more of the following:

- Reaction of similar nature having previously been observed with this type of medication.
- The event having often been reported in literature for similar types of medication.
- Subject’s underlying clinical state or other medical conditions
- Concomitant agents and/or therapies

The causal relationship, if any, to study medication will be defined by one of the following terms:

Assessment	Definition
Definitely	There is suspicion of a relationship between study medication and AE (without determining the extent of probability); there are no other more likely causes and study medication is suspected to have contributed to the AE
Probable	AE cannot be reasonably explained by other factors (i.e. clinical condition, environmental/toxic factors or other treatments)
Possible	AE can be reasonably explained by other factors (as mentioned above)
Unlikely	AE occurs within an unusual time frame of administration of study medication and can also be reasonably explained by other factors (as mentioned above)
Unrelated	There is no suspicion that there is a relationship between study medication and adverse event, there are other more likely causes and study medication is not suspected to have contributed to the AE

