11. STATISTICAL ANALYSIS

11.1 *Data acquisition and processing*

All clinical, neuroimaging volumetric and biomarker data will be collected sequentially and analyzed in a blinded fashion from coded samples. Data will be acquired prospectively and transcribed to the research database. For the imaging biomarker of ventricular volume the analysis will be performed only after completion of baseline or treatment periods, because the images need to be co-registered to the first acquired image. For biomarker data that can be acquired from cryopreserved biological samples, baseline and treatment data points will be evaluated simultaneously, to limit effect of inter-assay variation. Every effort will be made to have single rater/investigator to acquire one type of quantifiable clinical, neuroimaging and biomarker data for the entire cohort. Codes will be broken only after all pre-specified quantifiable data constituting primary and secondary outcomes are collected and recorded in the database.

11.2 *Statistical analyses of outcome measures*

Further details of the statistical analysis (e.g. definition of analysis populations) will be defined in a Statistical Analysis Plan which will be finalized before the database lock and opening of the treatment code.

Introduction

- a) For data collected only at 2 time-points (i.e. single collection during pre-treatment baseline and single collection at 1 year of therapy), such as CSF data, we will calculate for each individual %-change between baseline and therapy time-points
- b) For data collected every 6 months (i.e. clinical data and quantitative brain MRI data) we will calculate area under curve (AUC) for 3 data points obtained during pre-treatment baseline period and compare it to AUC for 5 data points obtained during the treatment period.

The rationale for using AUC (as opposed to linear regressions) is explained in detail in Figure 3:

[figure not shown]

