16. DATA AND SAFETY MONITORING

16.1 Monitoring plan for the study as a whole

This study will be monitored by a Data and Safety Monitoring Board (DSMB). [name] [name] is a board-certified neurologist with full clinical privileges. She will serve as the Independent Medical Monitor. [name] is independent of NIB and will be involved in crucial decision making regarding clinical issues that may arise during this trial. We are instituting an NIB independent medical monitor as a way to mitigate [name] conflict of interest (COI). [name], the PI on the study, is co-inventor on an NIH patent related to the use of idebenone and as such will receive patent royalty payments.

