18. ADVERSE EVENTS REPORTING

The Principal Investigator is responsible for detecting, documenting, and reporting unanticipated problems, adverse events (AEs), including serious adverse events (SAEs), and deviations in accordance with NIH policy, IRB requirements, and federal regulations. Relatedness to the research of all serious adverse events will be determined by the PI in consultation with the CD.

Serious unanticipated problems, serious adverse events (including deaths) that are not unanticipated problems, and serious protocol deviations will be reported to the IRB and CD as soon as possible and in writing on the Problem Report Form not more than 7 days after the PI first learns of the event, unless immediate reporting is waived for specific serious adverse events as noted below. Not serious unanticipated problems and not serious deviations will be reported to the IRB and CD as soon as possible and in writing on the Problem Report Form not more than 14 days after the PI first learns of the event.

All adverse events, deviations, and unanticipated problems will be summarized and reported at the time of Continuing Review.

The following expected Serious Adverse Events will not be reported to the IRB immediately and within 7 days unless they occur at a rate or severity greater than expected:

Hospitalization for urinary tract and kidney infections

Hospitalization for falls resulting in injury

These SAE's will be summarized at the time of continuing review. Serious adverse events occurring at a greater severity or frequency than expected will be reported as Unanticipated Problems as delineated above. The expected severity and frequency will be based upon each patient's pre-randomization history (baseline).

The NINDS, holder of the investigator-IND, or her/his representative is responsible for submitting reportable SAEs to the FDA under its private IND application, in accordance with Federal and NIH requirements. The NINDS is also responsible for providing Santhera Pharmaceuticals (Switzerland) Ltd. with copies of all Serious Adverse Drug Reaction reports concurrently with their submission to the FDA, including copies of any warning letters or other information affecting the safety and/or well-being of human subjects in research conducted under this CTA.

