22. CONFLICT OF INTEREST/TECHNOLOGY TRANSFER

NIH guidelines on conflict of interest have been distributed to all investigators.

[name] has identified a conflict of interest related to this study. She is one of the co-inventors on an NIH patent related to the use of idebenone as therapeutic agents in humans. This conflict of interest is properly disclosed in the protocol and in the consent form.

To resolve this conflict-of-interest, we have instituted following safeguards:

- [name] will not obtain informed consent and will not serve as the treating or evaluating physician on this protocol.

- [name], a senior NINDS neurologist who is not part of the NIB, will serve as the Independent Medical Monitor under this protocol.
- The independent DSMB will monitor the study.

No other investigators identified any additional conflicts of interest.

A clinical trial agreement (CTA#2009-0004) has been established with Santhera Pharmaceuticals through the NIH/NINDS office of technology transfer (OTT). This agreement specifies that Santhera will provide idebenone without restriction for the clinical study as outlined. All collected raw data will be the sole property of NINDS. Summary data will be made available to Santhera Inc. for regulatory purposes and for stock exchange purposes. Santhera Inc. can use these summary data for other purposes only after consultation with NINDS and only under confidentiality agreement.

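### After a positive pregnancy test, protocol 9.1.16 reveals the patient's arm to the investigators, with no visible exclusion of outcome raters or of those who judge causality

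*Protocol*

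**What the plan says.** Protocol 9.1.16 covers a pregnancy in the patient or in the patient's partner. Once it is confirmed, the patient stops drug and "his/her treatment assignment would be revealed to the investigators and the DSMB". No recipient is excluded and no request or decision is needed first.

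The same section deals with SAEs that a patient reports after month 24: such an event "will be subjected to expedited reporting only if judged to be related to the study treatment by the Investigator".

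On who rates and who judges:

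- Protocol 11.1 plans one person per type of data: "Every effort will be made to have single rater/investigator to acquire one type of quantifiable clinical, neuroimaging and biomarker data for the entire cohort".
- Protocol 9.2.20 gives causality to the investigator: "Every effort should be made by the investigator to explain each adverse event and assess its causal relationship".
- Protocol 18 gives SAE relatedness to the PI: "Relatedness to the research of all serious adverse events will be determined by the PI in consultation with the CD".
- Protocol 16.1 discloses that the PI "is co-inventor on an NIH patent related to the use of idebenone and as such will receive patent royalty payments".
- Protocol 22 lists safeguards for that conflict, among them that the person concerned "will not obtain informed consent and will not serve as the treating or evaluating physician on this protocol". Section 7.6.11 adds that "the PI will not serve as a clinical evaluator".

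Sections 7.4 and 7.6.12 hold the allocation code back from the investigators until the trial is complete and the databases are final or locked. Neither mentions a pregnancy exception.

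**The concern.** Unblinding one patient for a safety reason is normal. The difficulty is the breadth of the recipient list. As written, a person who later scores that patient, or who later decides whether an adverse event was caused by the drug, may be told the arm.

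The causality side is the more substantive of the two. A birth defect in a subject's offspring is an SAE under section 9.2.19, so the reveal can come before the very SAE most closely tied to its trigger. The PI, who decides relatedness with the CD, has a royalty interest in idebenone. The stated safeguards keep the PI away from consent, treatment and evaluation, but they do not cover relatedness calls or receipt of an assignment.

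**Working it through.** The plan states no figure on this point, so the check is mainly a comparison of texts, followed by a simple count.

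**1. Does stopping drug need the code?** No. Section 9.1.16 stops drug in any patient with a confirmed pregnancy, whichever arm the patient is in.

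**2. Whom does the word investigator cover?**

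- SAP 4.2: the investigator calculates the Scripps NRS, one of the four CombiWISE components.
- Protocol 11.1: a combined rater/investigator for each type of data.
- Protocol 7.6.11: investigators who analyse imaging and immunology data.
- Protocol 9.2.20: the investigator who assesses causality of adverse events.
- Protocol 18: the PI, with the CD, for SAE relatedness.

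This does not show that one person holds all these roles. It does show that the term cannot be taken to mean only a non-rating treating clinician.

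**3. Which results could be touched?**

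- *Primary AUC.* SAP 4.2 sets AUC values after premature discontinuation to missing. Reading a stop of study drug as such a discontinuation, later scores do not enter.
- *Sensitivity and secondary models.* SAP 13.1.2 and 13.2 use observed scores, so later ratings would enter if they exist. Protocol 9.3 asks for continued collection of outcomes off drug under the two MS safety criteria, but not under the pregnancy item. It promises follow-up until after the birth without mentioning ratings.
- *Safety reporting.* Section 9.1.16 requires SAEs up to the month 25 interview to be recorded and reported to the FDA, and states no relatedness condition. Section 18 sends SAEs to the IRB within 7 days, apart from two listed kinds of expected hospitalisation. Sections 16.2.5 and 16.3 send all SAEs to the DSMB. Section 9.3 requires a patient's pregnancy to be reported to the IRB at once and the infant's status at 8 to 12 weeks to be collected. The relatedness call decides only expedited reporting of SAEs reported after month 24, and even that overlaps with the month 25 rule.

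**4. Size.**

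- Patients directly affected per event: 1/66 = 1.5%.
- Scheduled post-baseline scores in the MMRM: 66 × 4 (months 6, 12, 18, 24) = 264.
- Scheduled scores in the random coefficient model: 66 × 7 (months -12, -6, 0, 6, 12, 18, 24) = 462.
- Assumption, not from the documents: the pregnancy is found 1 to 6 months into 9. Follow-up to birth is then 9 − 1 = 8 down to 9 − 6 = 3 months. With visits 6 months apart, 8 months hold 1 or 2 visits and 3 months hold 0 or 1, so at most 2 ratings.
- Ceiling on that assumption: 2/264 = 0.8% (MMRM) and 2/462 = 0.4% (random coefficient model).
- Without that assumption, one patient has at most 4 post-baseline scores: 4/264 = 1.5% and 4/462 = 0.9%.

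These are ceilings on ratings that the plan does not require. The documents give no pregnancy rate, and section 12.3 requires contraception, so no expected number of events is calculated.

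**The case against.** The strongest objection is that roles may be settled elsewhere. Section 12.4 (Qualifications of investigators) was not available to check, and section 15 shows that it assigns at least the consent role. It may also separate raters from treating clinicians. That stands, and it is why the point is limited to the visible text.

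Second, there is a care reason to know the exposure. The research team counsels and follows the patient or partner, and knowing that a patient took placebo would inform a relatedness judgement. This also stands, but it supports telling a clinician and the DSMB, not every investigator. The DSMB can read a blinded call together with the arm, so the information is not lost.

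Third, the PI's conflict has its own mitigation: the Independent Medical Monitor, the DSMB and consultation with the CD. That lowers the risk. It does not limit who receives the assignment.

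Some stronger readings are tempting and are not supported:

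- *The block partner is unblinded too, because blocks have size 2.* That needs a rater who knows the randomisation order within the age stratum. The documents do not show this.
- *A birth defect could go unreported.* The reporting routes set out above do not generally depend on the relatedness call.
- *Section 16.3 already provides a restricted route for SAEs.* It lets the DSMB request unblinding, but does not say that investigators stay blinded.
- *The PI rates outcomes.* Section 7.6.11 rules out clinical evaluation by the PI.

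**Conclusion.** The point holds as a minor weakness of wording. On the visible text, 9.1.16 gives the arm to a group that can include outcome raters and causality assessors, when stopping drug does not require it.

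The size is one patient per event. A reader might infer a threat to the primary result; the documents do not support that, because AUC values after discontinuation are set to missing. What remains is the relatedness call on a later SAE in that patient, plus any later ratings in sensitivity and secondary analyses.

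This rests on three conditions: that section 12.4 does not already restrict the roles, that a stop of study drug counts as premature discontinuation for the AUC rule, and that any ratings are collected after the reveal at all. Section 7.6.10 reports that data analysis is complete, so the wording matters mainly if the protocol is re-used.

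**What to change.** In 9.1.16, release the single-patient allocation only to the DSMB, the Independent Medical Monitor and, where care of the pregnancy requires it, a clinician who does not rate outcomes. State that outcome raters stay blinded. Have the investigator or PI judge the relatedness of any later SAE without the arm, with the DSMB reading that call alongside the arm. As housekeeping, cross-refer to this exception in 7.4 and 7.6.12.

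For this completed trial, the useful step is to report whether any such reveal took place and which roles were told.

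The cost is wording only, using the existing medical monitor, DSMB and pharmacy. The downside is one extra contact step before the treating clinician learns the arm; stopping drug is not delayed.
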